| 1. To evaluate clinical activity after treatment with GSK2879552, alone or in combination with azacitidine, in adult subjects with HR MDS previously treated with HMA. | 1. Clinical benefit rate (CBR) defined as % of subjects achieving CR, mCR, PR, cytogenetic response, HI or SD. Objective response rate (ORR) defined as % of subjects achieving CR, mCR, PR, cytogenetic response, or HI [as per 2006 IWG criteria]). |
| Secondary | |
| 1. To further evaluate the safety and tolerability of GSK2879552 administered alone or in combination with azacitidine. | 1. Changes in safety parameters: e.g. AEs and SAEs, changes in laboratory values, vital signs, electrocardiograms [ECGs], and physical examinations. |
| 2. To characterize the population PK of GSK2879552, alone or in combination with azacitidine in patients with HR MDS previously treated with HMA. | 2. Population PK parameters for GSK2879552 such as clearance (CL/F). |
| 3. To evaluate duration of response, duration of clinical benefit, progression-free survival, and overall survival. | 3. Duration of response (DOR) defined as the time from first documented response to disease progression. Progression free survival (PFS) defined as the time from first dosing day to disease progression or death from any cause. Overall survival (OS) defined as the time from first dosing day until death from any cause. |
| 4. To evaluate frequency and time to progression to AML (per 2006 IWG criteria) | 4. Proportion of subjects with disease progression to AML. Time to AML progression. |
| 5. To evaluate platelet and RBC transfusion dependence. | 5. Number of documented platelet and RBC transfusions per month within 3 months prior to study entry and while on study. |

| Objectives | Endpoints |
|---|--|
| Exploratory | |

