4.2. Treatment Schedule and Duration

Treatment with GSK2879552 in both arms will be administered orally as continuous daily dosing until progression. Azacitidine will be administered at 75 mg/m² on days 1-7 of each 28 day cycle by intravenous (iv) infusion or subcutaneous (sc) injection (route of administration: by physicians choice). Subcutaneous administration will be required during the first cycle as PK information will be collected.

Alterations to the dose and schedule of GSK2879552 may be incorporated based on emerging safety, tolerability, and PK data. The dose and schedule of azacitidine may be also altered based on emerging safety, tolerability and PK data. Azacitidine dosing on Mon-Fri (Days 1-5) and Mon-Tue (Days 8-9) may be allowed on a case by case basis.

Subjects may continue treatment in the study until disease progression, unacceptable toxicity, or withdrawal of consent. Subjects experiencing disease progression on mono therapy (Arm A) will be allowed to cross over to be treated with the combination (Arm B) once the RP2D has been established. All subjects will be followed after study treatment discontinuation until death, lost to follow-up or withdrawal of consent. The duration of the study will depend on recruitment rates, and timing of subject's duration on study. Subjects may be allowed to continue on study treatment after disease progression if the Investigator, in consultation with the sponsor's Medical Monitor, determines that continuing treatment will benefit the patient.

4.3. Part 1

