4.7. Permanent Discontinuation of Study Treatment

Subjects will receive study treatment until disease progression (according to IWG), death, withdrawal of consent, or unacceptable toxicity, including meeting stopping criteria for liver chemistry. The investigator may discuss with a GSK Medical Monitor continuing a subject who is receiving clinical benefit but has met the formal criteria for disease progression, if the following criteria are met: Investigator-determined clinical benefit (e.g. symptomatic improvement), lack of significant toxicity (no drug related non-

hematologic grade 3/4 AEs within the last 4 weeks) and no therapeutic alternatives expected to provide durable responses.

In addition, study treatment may be permanently discontinued for any of the following reasons:

- Substantial deviation(s) from the protocol
- Request of the subject or proxy (withdrawal of consent by subject or proxy)
- Investigator's discretion
- A clinically significant adverse event leading to an interruption of treatment for greater than 14 days. If the investigator and GSK Medical Monitor conclude that the benefit: risk is positive and supports continued treatment in a subject who has had a > 14 day treatment delay, then the subject may continue therapy with the approval of the GSK Medical Monitor on case by case basis.
- Persistent G4 thrombocytopenia for >4 weeks not attributed to disease or requires platelet transfusions for bleeding in the absence of the disease
- Intercurrent illness that prevents further administration of study treatment(s)
- Subject is lost to follow-up.
- Study is closed or terminated.

Once a subject has permanently discontinued study treatment, the subject will not be allowed to re-enter this study. All subjects who discontinue from study treatment will have safety assessments at the time of discontinuation and during post-study treatment monthly follow-up.

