9.3. Data Analysis Considerations

9.3.1. Analysis Populations

All Treated Subjects Population: This will consist of all subjects who received at least one dose of study treatment. Safety and clinical activity data will be evaluated based on this population.

The Pharmacokinetic Population: This will consist of those subjects in All Subjects Population and for whom a PK sample is obtained and analyzed.

The Crossover Population will comprise the subset of subjects in Part 1 and Part 2 who had intra-subject Arm A to Arm B crossover. It will be the primary population when summarizing data in Part 1, Part 2 crossover phase.

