9.4. Key Elements of Analysis Plan

Data will be listed and summarized according to the GSK reporting standards, where applicable. Data will be listed and summarized mostly by doses. Separate analyses will be provided for Part I and in Part II where applicable. In some instances, analysis may also be generated based on the dose of GSK2879552. Data from Part I and Part II may be combined for some analyses at the end of the trial, for subjects treated at the same dose level. Complete details will be documented in the Reporting and Analysis Plan (RAP). Any deviations from, or additions to, the original analysis plan described in this protocol will be documented in the RAP and final study report.

As it is anticipated that accrual will be spread thinly across centers and summaries of data by center would unlikely be informative, therefore data from all participating centers will be pooled prior to analysis.

All data up to the time of study completion/withdrawal from study will be included in the analysis, regardless of duration of treatment.

As the duration of treatment for a given subject will depend on efficacy and tolerability, the duration of follow-up will vary between subjects. Consequently there will be no imputation for missing data.

Demographic and baseline characteristics will be summarized.

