9.4.1. Clinical Activity Analyses

The clinical benefit rate (CBR) is defined as the percentage of subjects with a Complete Remission (CR), marrow complete remission (mCR) or a Partial Remission (PR) or a Hematologic Improvement (HI) or Stable Disease (SD) at any time as per disease-specific criteria ([Appendix 5](#) and [Appendix 6](#)). Subjects with unknown or missing response will be treated as non-responders, i.e. these subjects will be included in the denominator when calculating the percentage. The number and types of responses, as outlined in IWG criteria [[Cheson, 2006](#)], will be listed and summarized separately, as appropriate.

The ORR will be reported at the interim and final analysis for each arm specified in Part 2 as well as all evaluable subjects in Part 1 treated at or above RP2D. Part 1 and Part 2 subjects who received the same dose within the same treatment arm may be combined together in the analysis. The estimates along with 95% exact confidence interval (CI) will be provided.

The CBR and ORR differences between the two cohorts will be provided along with corresponding 95% CI. A chi-square test will be used to test for differences between arms if data warrant.

Duration of response is defined as the subset of subjects who show a response (CR, mCR, PR, or HI), the time from first documented evidence of response until the first documented sign of disease progression or death. Duration of response will be summarized descriptively for each arm, if data warrant, using Kaplan-Meier medians and quartiles. Details on rules for censoring will be provided in the RAP.

For the analysis of **Progression-free survival (PFS)**, if the subject received subsequent anti-cancer therapy prior to the date of documented events, PFS will be censored at the last adequate assessment (e.g. assessment where visit level response is CR, mCR, PR, HI or SD) prior to the initiation of therapy. Progressive disease (PD) will also be defined per standard criteria. Otherwise, if the subject does not have a documented date of events, PFS will be censored at the date of the last adequate assessment. Further details on rules for censoring will be provided in the RAP. PFS will be summarized by arm and dose using Kaplan-Meier quantile estimates along with 2-sided 95% CIs at the time of final analysis, if data warrant.

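### The response window for CBR (and, by omission, ORR) has no end at progression, so a subject who progresses first and stays on the assigned treatment can later be counted as a success

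*Protocol*

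**What the plan says.** **Counting rule.** Section 9.4.1 defines CBR as the percentage of subjects with CR, mCR, PR, HI "or Stable Disease (SD) at any time as per disease-specific criteria". For ORR, Section 3 gives only the qualifying categories: "Objective response rate (ORR) defined as % of subjects achieving CR, mCR, PR, cytogenetic response, or HI". No time limit is attached to it.

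**Data and population.** Section 9.4 states: "All data up to the time of study completion/withdrawal from study will be included in the analysis, regardless of duration of treatment". Section 9.3.1 assigns activity analyses to All Treated Subjects: "Safety and clinical activity data will be evaluated based on this population".

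**Treatment after progression.** Section 4.2: "Subjects may be allowed to continue on study treatment after disease progression if the Investigator, in consultation with the sponsor's Medical Monitor" agrees that the patient would benefit. Section 4.7 describes the same option, "continuing a subject who is receiving clinical benefit but has met the formal criteria for disease progression", subject to conditions on benefit, toxicity and alternatives. Neither section limits it to one arm. The Time and Events tables schedule a disease assessment on Day 1 of each cycle from Cycle 2.

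**Neighbouring endpoints.** PFS ends at progression or death (Section 3). Section 9.4.1 adds a new-therapy rule: "if the subject received subsequent anti-cancer therapy prior to the date of documented events, PFS will be censored". Duration of response in 9.4.1 runs from first documented response to the first documented sign of progression or death.

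**Decision rule.** Section 9.1.2 rejects the 30% null with at least 12 of 28 responders per arm. Section 9.2.1 states a type I error of 0.099 and 81% power.

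**The concern.** Nothing in the protocol closes the response window at first progression. A subject whose first outcome is progression, and who is kept on the assigned treatment, goes on being assessed every cycle. Each assessment is another chance to meet a success category of the tested endpoint.

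Three things are at stake.

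- **Coherence.** The same subject can be an early PFS event and a CBR success. Duration of response has no meaning for that subject, because the first sign of progression comes before the first response. The protocol's own duration definition presupposes that response precedes progression.
- **Direction.** The rule can add successes but cannot remove any, so CBR and ORR can only go up.
- **Open-label influence.** The decision to continue a progressed subject rests on investigator-judged benefit and a discussion with the Medical Monitor. That decision determines who gets further chances to score.

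This is separate from the Arm A to Arm B crossover, for which Section 4.6 sets a new baseline and Section 9.3.1 a separate population. Subjects who continue on their assigned treatment, including everyone in Arm B, have neither.

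**Working it through.** **1. Reproduce the plan's own figures.** Inputs from Section 9.1.2 (Table 5) and Section 9.2.1: stop if responses are ≤ 1, 2, 3, 3, 4, 5, 6, 8, 9, 11 at n = 10, 12, 14, …, 28; success is ≥ 12 of 28; null 0.30, target 0.50. An exact binomial recursion through these bounds gives:

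| Quantity | Recomputed | Stated |
|---|---|---|
| Type I error (p = 0.30) | 0.0991 | 0.099 |
| Power (p = 0.50) | 0.8174 | 81% |
| Termination at p = 0.30 | 0.9009 | 0.90 |
| Termination at p = 0.50 | 0.1826 | 0.183 |

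The continuation probabilities for n = 10 to 26 match Table 5 to four decimals. The design arithmetic is correct; the question is only what counts as a response.

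**2. Which subjects can be reclassified.**

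- *Stable disease:* Appendix 10 requires more than 8 weeks without progression. A subject who had that before progressing already counts, and a first-outcome progressor does not naturally meet it later. This route is largely closed.
- *HI:* as printed in Appendix 10 it can rest on one lineage and carries no minimum duration. Progression can also be called on counts or transfusion dependence. The scheduled blood counts are enough to find HI, so this is the easiest route.
- *CR, mCR, PR, cytogenetic response:* possible, but CR, mCR and PR need a marrow, which is done only when clinically indicated or to confirm a response (Section 7.4). Cytogenetic response is in the Section 3 definitions, though not in the 9.4.1 list for CBR.
- *New anti-cancer therapy:* not excluded by the wording, but narrow. Section 6.11.2 bars it during treatment, and the two-monthly follow-up is by chart or phone for survival, PFS data and new treatment.

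**3. Effect of one subject.** 1/28 = 0.0357, or 3.6 percentage points. Against the assumed effect of 0.50 − 0.30 = 0.20, that is 0.0357/0.20 = 18%.

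**4. Effect on the false-positive rate.** Let q be the share of true non-benefiters who are later credited. The protocol gives no value for q, so it is an assumption. If the true rate of benefit before progression is 0.30, the counted rate is 0.30 + 0.70q. The same recursion gives:

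| q (assumed) | Counted rate | Subjects of 28 (28 × 0.70q) | P(success) |
|---|---|---|---|
| 0 | 0.300 | 0 | 0.099 |
| 1% | 0.307 | 0.20 | 0.114 |
| 2% | 0.314 | 0.39 | 0.131 |
| 3% | 0.321 | 0.59 | 0.149 |

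In terms of mechanism, q is the share of failures continued after progression times the share of those later scored as benefit. For example, 10% × 10% = 1% and 30% × 10% = 3%.

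**The case against.** **The null may already be defined this way.** No passage says the test concerns benefit before progression. If CBR as literally defined is at most 30%, the type I error remains 0.099. The protocol does not say how the 30% historical rate was counted. This stands: the inflation in step 4 is conditional on reading the null as pre-progression benefit. The PFS and duration-of-response inconsistencies do not depend on that reading.

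**Few subjects are affected.** Section 4.7 restricts continuation to subjects with judged benefit, no significant toxicity and no alternatives. Some of them will already be successes, and Arm A progressors may cross over instead. Section 2.1.2 cites median survival of 4.3 to 5.6 months after HMA failure. This stands as a limit on size, and it is why the illustration uses small values of q.

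**A cut-off may discard real responses.** The study drug lowers platelets, counts recover after interruption (Section 2.2.4), and azacitidine responses can be late (Section 2.2.6). A count-based progression might therefore precede a genuine response. This is a real downside, but PFS already uses the same progression criteria, and a separate table keeps such responses visible.

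**It belongs in the RAP.** Section 9.4 sends complete details there. For ORR, where the protocol is merely silent, that has some force. For CBR the protocol fixes the window itself, so a RAP cut-off would have to narrow the protocol's own words.

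**Stronger readings to avoid.** A reader might infer that both endpoints are expressly open-ended, that responses to later therapy will commonly be counted, or that late stable disease will add successes. The documents do not support these: the open-ended wording is attached to CBR only, the new-therapy route has no scheduled response assessment after treatment ends, and the stable-disease criterion largely excludes early progressors. Section 9.1.2 also refers in one place to a confirmed response rate, so an isolated single-count HI is not certain to be accepted.

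**Conclusion.** The point holds for treatment beyond progression within the assigned arm. For CBR it follows from a stated rule; for ORR it follows from the absence of any window together with the all-data rule. The subjects at issue are early progressors who stay on treatment and later reach HI, mCR, PR, CR or cytogenetic response. For them CBR or ORR conflicts with PFS, and duration of response is undefined.

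The direction is certain and the size is not. One subject is 3.6 points, which can decide the result when the observed count lies at the 12-of-28 boundary. The type I error figures of 0.114 to 0.149 are illustrations. They rest on an assumed reclassification rate of 1% to 3% and on the null meaning benefit before progression. They are not evidence that the error rate is in fact inflated by that amount. The change should be made because the rule is inconsistent with its neighbours and inexpensive to correct.

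**What to change.** In Section 9.4.1, and for the counts used with Table 5, replace the open-ended wording with: *best response from first dose up to the first documented IWG progression or the start of subsequent anti-cancer therapy (including crossover), whichever is earlier*. Apply it to both CBR and ORR, and carry it into the RAP. Report responses seen during treatment beyond progression in a separate descriptive table.

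The cost is one sentence in the protocol and its counterpart in the RAP. No new data are needed, and the rules for continuing treatment are untouched. The downside is that CBR and ORR may be slightly lower, and a late response after an early count-based progression moves from the primary count to the descriptive table.

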9.4.2. Safety Analyses

The All Treated Subjects Population will be used for the analysis of safety data. All serially collected safety endpoints (e.g. laboratory tests, vital signs, electrocardiogram [ECGs]) will be summarized according to the scheduled, nominal visit at which they were collected and across all on-treatment time points using a “worst-case” analysis. Complete details of the safety analyses will be provided in the Reporting and Analysis Plan (RAP).

Complete details of the safety analyses will be provided in the RAP.

A listing by subject including treatment administered, and compliance, will be generated with dates and times of treatment administered. The number of subjects exposed to study drug will be tabulated for Part 1 (for each dose cohort) and Part 2.

All relevant safety data will be listed and summarized according to IDSL standards. The reporting and analysis plan will list the IDSL templates for the displays. Adverse events will be coded and grouped by system organ class (SOC) and preferred (coded) term (PT) using the Medical Dictionary for Regulatory Activities (MedDRA) system for adverse event coding. AEs will be graded according to the National Cancer Institute Common Terminology Criteria for Adverse Events (NCI CTCAE) Version 4.03. Adverse events will be summarized by maximum toxicity grade for each initial dose level. All AEs will be listed. A summary of the number and percent of subjects reporting each AE at least once will be produced for all AEs, for drug-related AEs and for SAEs for Part 1 (for each dose cohort) and Part 2. A listing of those AEs identified as dose-limiting toxicities will also be produced for each dose cohort for Part 1. A listing showing the relationship of AE verbatim text to group terms and body systems will also be produced. A listing of withdrawals due to AEs will be provided. Deaths and SAEs will be listed should they occur.

Clinical laboratory evaluations will be performed on the days specified in the Time and Events Table. Clinical chemistry, coagulation, hematology and urinalysis values and change from baseline values will be listed for each subject and flagged high or low relative to their normal ranges, where applicable. The toxicity grade for laboratory data will be calculated using NCI CTCAE Version 4.03. The lab data will then be summarized according to the subject’s baseline grade and maximum grade for each cycle of therapy. A listing of subjects with potentially clinically important lab abnormalities will also be produced. A summary of lab values and change from (baseline) may be done for Part 1 (for each dose cohort) and Part 2.

Vital signs and ECG data will be listed and summarized for Part 1 (for each dose cohort) and Part 2. Changes from baseline will be included in the listings and summary.

ECOG Performance Status assessments will be listed and summarized for Part 1 (for each dose cohort) and Part 2.

9.4.2.1. Extent of Exposure

The number of subjects administered study treatment will be summarized according to the duration of therapy.

Extent of exposure of GSK2879552 and azacitidine will depend on tolerability of the subjects to the doses administered and the course of their disease. The number of subjects exposed to GSK2879552 and azacitidine will be summarized for each dose level administered.

9.4.2.2. Adverse Events

Adverse events (AEs) will be coded using the standard MedDRA and grouped by system organ class. Adverse events (AEs) will be graded by the investigator according to the National Cancer Institute- Common Toxicity Criteria for Adverse Events (NCI-CTCAE), (version 4.03).

Events will be summarized by frequency and proportion of total subjects, by system organ class and preferred term. Separate summaries will be given for all AEs, treatment-related AEs, serious adverse events (SAEs) and AEs leading to discontinuation of study treatment. Adverse events (AEs), if listed in the NCI-CTCAE (version 4.03) will be summarized by the maximum grade. Otherwise, the AEs will be summarized by maximum intensity.

AEs of special interest will be outlined in the RAP.

The incidence of deaths and the primary cause of death will be summarized.

9.4.2.3. Clinical Laboratory Evaluations

Hematology and clinical chemistry data will be summarized using frequencies and proportions according to National Cancer Institute-Common Toxicity Criteria for Adverse Events (NCI-CTCAE) (version 4.03). Laboratory test results outside the reference ranges that do not have an associated NCI-CTCAE criterion will be summarized using proportions. Further details will be provided in the Reporting and Analysis Plan (RAP).

9.4.2.4. Other Safety Measures

Data for vital signs and electrocardiograms (ECGs) will be summarized based on predetermined criteria identified to be of potential clinical concern (PCI). Further details will be provided in the Reporting and Analysis Plan (RAP).

